The steering committee will work with the patient partner and the patient advisory group to ensure that the language describing the metrics is understandable to a general audience with at least grade six education, particularly for the process metrics. Within the Delphi survey, for each metric there will be a brief description of what it is and why it might be important, and expandable links for further explanation and details for each metric (e.g., the items for a patient-reported outcome or experience measure), as deemed necessary by the steering committee.

Stage 2. Modified Delphi consensus process

Study Population

We aim to recruit 77 participants with the following characteristics (accounting for 30% attrition rate (9,17)):

- 26 anesthesiologists
- 26 patients and/or their family members/caregivers
- 9 surgeons, one from each of the following specialties (may include clinician-researchers):
 - General surgery
 - Neurosurgery
 - Obstetrics and gynecology
 - Orthopedic surgery
 - Otolaryngology
 - Plastic surgery
 - Thoracic surgery
 - Urology
 - Vascular surgery
- 4 nurses
- 8 physicians: 2 each from internal medicine, emergency department, family practice, family practice anesthetists
- 4 health administrators or quality improvement leads

Inclusion Criteria: Adult participants aged 18 and above will be included. Patient/family participants must have undergone a surgical experience within the past three years, and have the capacity to provide informed consent. All other participants must be actively practising in Canada in the disciplines they represent.

Exclusion Criteria: Participants with self-declared conflicts of interest with this project.

While the study will primarily be conducted in English using BC Children's Hospital Research Institute's REDCap survey system (18,19), to ensure representation, participants will not be excluded based on language or technology limitations. During recruitment, patients could indicate accommodations required, including translation and submitting study materials through postal mail. The steering committee will review the degree to which accommodations would be feasible within the human resources and study budget.

Development of a standardized set of core metrics to assess the quality of anesthesia, perioperative care, and acute pain management in Canada: scoping review and multidisciplinary consensus Delphi study

Recruitment, consent, panel selection, and withdrawal

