Interested participants will be invited to complete a study information and eligibility check survey in REDCap, which will be available via a shared public link. This survey will present study information that will allow them to confirm their eligibility, and establish their willingness and ability to participate, before submitting their preferred contact email address, which will be used to route all subsequent surveys.

Participant data will be de-identified using study ID throughout the study. The participant will be informed that de-identified results from the eligibility survey will be collected to report the study inclusion/exclusion flow, and that if they do not want these data collected then they should not fill the eligibility survey.

A participant can withdraw from the study and/or their consent to data sharing for research at any time. If this happened prior to the start of the Delphi Round 1, the research team will attempt to recruit replacement(s) if possible.

Development of a standardized set of core metrics to assess the quality of anesthesia, perioperative care, and acute pain management in Canada: scoping review and multidisciplinary consensus Delphi study

Participants who completed all components of the study (demographics survey and Delphi) will each receive an electronic gift card of \$75 by email as honorarium); those who only complete the initial round will receive an electronic gift card of \$25.

Full demographics survey

After providing electronic informed consent, a full demographics survey will be sent to each participant for completion within two weeks. This is based on previous methodology and will include age (in decades), sex, gender, race/ethnicity, and geographical category (urban, semi-urban, rural) of hospital they most frequently interact with for the purposes of surgeries. For patients and/or family members only, we will also ask about their highest education level (grade school, high school, diploma or undergraduate degree, postgraduate degree), income (by Canadian tax brackets), ethnicity, home community location if different from the hospital location (urban, semi-urban, rural), occupation, and type(s) of surgery. For health professionals, we will also ask about primary practice area, years in practice (<5, 5-9, 10-19, >20 yrs), subspecialty training, practice setting (academic, community), and involvement in any of research, quality assurance/improvement, or teaching continuing medical education.

Delphi process

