
The multidisciplinary panel of participants will iteratively review the list of candidate metrics using a modified Delphi process. While specific guidance on consensus thresholds and the optimal scales are limited, the design will follow best practices from literature (3,6-11). In the last Delphi cycle, the panel will be asked to select the most essential items to include into a core set of metrics.

Independent, anonymous voting using REDCap over three rounds will be used to identify the most important metrics to define the quality of anesthetic care. Each round will be coordinated through the Department of Anesthesiology, Pharmacology and Therapeutics, Faculty of Medicine, UBC.

Participants will be given at least two weeks of notice about an upcoming round, and will have two weeks to complete the REDCap survey for a given round. Reminder emails will be sent 7 and 14 days after the survey opens to those who have not yet completed it. If a survey is still not completed, up to two additional reminders will be sent once a week, and if still no response, the round will be closed. The participant who missed a round will still be able to participate in future rounds. There will be at least two weeks between each round to provide time for the steering committee to analyze the data and prepare for the next round. Additional cycles (beyond the 3rd) may be performed if the objectives have not been achieved.

Delphi Round 1

The initial list of metrics and descriptions from the scoping review will be presented. Participants will independently score each of the listed metrics for importance on a five-point scale (from '1=not at all important' to '5=very important') (8). Participants may also enter comments in free-text if they have any specific feedback or suggestions on a given item, which will be summarized and shared with participants in Round 2. The mean and median scores for each metric will be calculated for overall panel and for subgroups of 1)

Development of a standardized set of core metrics to assess the quality of anesthesia, perioperative care, and acute pain management in Canada: scoping review and multidisciplinary consensus Delphi study

patient/caregiver and 2) health provider groups, and will also be presented in Round 2. Metrics receiving a mean score ≥ 4 by $\geq 65\%$ of each subgroup and ≤ 2 by $<20\%$ of the subgroups will be retained for voting in Round 2 (8).

Delphi Round 2

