Participants will score each metric using the same scale as in Round 1, and suggest revisions or comments as needed. Metrics receiving a mean score ≥ 4 by $\geq 65\%$ of each subgroup and ≤ 2 by $<20\%$ of the subgroups will be retained for voting and prioritizing in Round 3.

Delphi Round 3

Prior to Round 3, the study team will review the list of metrics, and aggregate and/or refine their wording as needed. Participants will be presented with a list of metrics with mean and standard deviation scores from the Likert scales, and be asked to vote on which metrics consist of a core set of problems (i.e., must be addressed by the health system as a priority) using a three-point scale of “definitely priority”, “equivocal (either way)”, and “not a priority” (10,20). Metrics where $>70\%$ participants voted “definite” will be marked in the publication as the core metric set. If no consensus is reached, there may be additional rounds of rating using a smaller sample of participants.

Statistical analysis

Analysis will be performed using R (R Foundation for Statistical Computing, Vienna, Austria). Cohort characteristics will be reported using descriptive statistics. Each round of Delphi will be analyzed as described above, and presented both as an overall group and as individual subgroups.

Sample size calculation

There is limited guidance regarding sample size for Delphi processes, but, in general, the key is to choose a broad representation from key stakeholders with a margin of safety built in for possible attrition. Delphi studies often involve a total of 17 members (9) and that adding more participants above 23 did not alter the consensus results (21). We have aimed for broad representation across all the key stakeholder groups. Thus, we chose $n = 20$ for each of the groups of anesthesiologists and patients. We chose the number of surgeons to represent the primary set of noncardiac surgical specialties. We also accounted for an attrition rate of 30% per literature (9,17) to ensure that there will be sufficient representation in the last cycle despite attrition.

Impact and future directions

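### At the plan's own 30% attrition, recruiting 26 per main group leaves about 18 rather than the chosen 20, and the nine surgeons carry no attrition allowance

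*Combined protocol and SAP*

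**What the plan says.** The panel size is set in two places in the protocol.

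- **Sample size calculation.** A size of 20 is chosen "for each of the groups of anesthesiologists and patients". Surgeons have a different basis: "We chose the number of surgeons to represent the primary set of noncardiac surgical specialties". The attrition statement follows: "We also accounted for an attrition rate of 30% per literature (9,17) to ensure that there will be sufficient representation in the last cycle".
- **Stage 2, Study Population.** The list opens with "We aim to recruit 77 participants with the following characteristics (accounting for 30% attrition rate". Under it stand 26 anesthesiologists, "26 patients and/or their family members/caregivers", "9 surgeons, one from each of the following specialties" (nine specialties are named), 4 nurses, 8 other physicians and 4 administrators or quality improvement leads.

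Two further provisions bear on attrition. On withdrawals, the section on recruitment, consent, panel selection and withdrawal says: "If this happened prior to the start of the Delphi Round 1, the research team will attempt to recruit replacement(s) if possible". On non-response, the Delphi process section says: "The participant who missed a round will still be able to participate in future rounds".

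**The concern.** A reader of these two sections will conclude that 20 anesthesiologists and 20 patients remain in the last round after a 30% loss, and that the whole panel of 77 carries an allowance for that loss. Neither follows from the printed numbers. The 26 looks like 20 increased by 30%, which is not the inverse of losing 30%. The surgeon count equals the number of specialties, so it leaves no room for any loss.

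What is at stake is representation in the final round, which is the plan's own reason for the allowance. A surgeon who leaves after Round 1 has started takes the only voice of a specialty with them, because no replacement is planned from that point.

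**Working it through.** **Inputs.** Chosen size 20 per main group, and attrition of 30% aimed at the last cycle (Sample size calculation). Recruitment of 26, 26, 9, 4, 8 and 4 (Study Population). The 30% is read as cumulative loss by the last round.

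**Reproducing the plan's figures.**
- Total: 26 + 26 + 9 + 4 + 8 + 4 = 77, as stated.
- Main group: the formula is not printed, but n × (1 + d) = 20 × 1.3 = 26 matches exactly. The form that keeps n after a loss d is n/(1 − d) = 20/0.7 = 28.6, so 29, which does not match.

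**What 26 per main group delivers.** Expected number remaining = 26 × (1 − d):

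| Attrition | Left of 26 | Left of 9 surgeons |
|---|---|---|
| 10% | 23.4 | 8.1 |
| 20% | 20.8 | 7.2 |
| 30% | 18.2 | 6.3 |

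The break-even rate for keeping 20 is (26 − 20)/26 = 23.1%. The shortfall at 30% is 20 − 18.2 = 1.8 people per group.

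**Surgeons.** Nine specialties at one each gives nine before any allowance. Either formula would give more: 9 × 1.3 = 11.7, or 9/0.7 = 12.9. At 30% loss, 9 × 0.7 = 6.3 remain, so about three specialties have no one in the last round.

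**Could the 77 still contain an allowance for surgeons?** Assumed bases of 20 + 20 + 7 + 3 + 6 + 3 = 59 give 59 × 1.3 = 76.7, which rounds to 77. But seven surgeons cannot cover nine specialties at one each, so this reading conflicts with the stated basis for the surgeon number. No pre-attrition figure is printed for nurses, other physicians or administrators, so nothing is concluded about those groups.

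**Effect on the votes.**
- Pooled Round 3 rule (more than 70%): 77 × 0.7 = 53.9 voters. With 29 per main group the panel is 29 + 29 + 9 + 4 + 8 + 4 = 83, leaving 83 × 0.7 = 58.1. The standard error of a 70% proportion is √(0.21/54) = 6.2 points against √(0.21/58) = 6.0 points.
- Patient/caregiver subgroup (65% rule in Rounds 1 and 2): even if the full 30% were already lost by then, the standard error of a 65% proportion is √(0.2275/18) = 11.2 points, against √(0.2275/20) = 10.7 points with 20.

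**The case against.** The strongest reply is that the plan never calls 20 a number of completers. It asks only for sufficient representation in the last cycle and puts no number on that. The benchmarks it cites are a typical panel of 17 and no change in consensus above 23. At 30% loss about 54 people remain overall, above both, and about 18 remain in each main group. This stands as a reason to call the impact small. It does not rescue the stated sizes: 20 is the only pre-attrition figure printed, and the attrition allowance is the only reason given for recruiting more than 20. If a number other than 20 was meant to remain, the plan should state it.

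A second reply is that the attrition phrase is attached to the total, and that the Sample size calculation openly gives specialty coverage as the basis for the surgeons. That is fair, and it narrows the point: the phrase does not fit the surgeon line listed beneath it. No decision rule uses surgeons as a subgroup, and metrics specific to one surgery are excluded, so no voting result is shown to change.

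Third, the plan does not say whether 30% is cumulative or per round. The reference to the last cycle supports cumulative, which is also the milder reading. A 30% loss at each of the two intervals between three rounds would leave 26 × 0.7 × 0.7 = 12.7.

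Finally, reminders, the $75 completion honorarium and the right to return after a missed round may keep attrition below 30%. That may prove true, but the plan chose 30% as its planning rate.

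**Conclusion.** The concern holds on both parts. Recruiting 26 per main group does not keep 20 at the plan's own attrition rate: it leaves about 18, and 20 is kept only at 23.1% or less. The nine surgeons include no allowance, although the total of 77 is presented as accounting for attrition; about 6 of 9 would be expected in the last round.

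The size is modest. The shortfall is about two people per main group, there is no powered test, and the precision of the votes hardly changes. The loss of single-member specialties bears more directly on the plan's aim of broad representation. The conclusion rests on reading 20 as the number meant to remain and 30% as cumulative loss. The retained numbers are expected values, with no dropout distribution assumed. The correction should be made because the justification is wrong as written; the validity of the consensus is not in question.

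**What to change.** Restate the expected numbers in both Study Population and Sample size calculation, for example:

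> Recruiting 26 per main group gives an expected 18 per group in the last round at 30% attrition; 20 per group is kept only if attrition is 23% or less. The surgeon number carries no attrition allowance: one per specialty is the aim at recruitment, and about 6 of 9 are expected in the last round at 30% attrition.

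This text should replace or qualify the attrition phrase attached to the 77 in Study Population and the attrition sentence in Sample size calculation. If those stay unchanged, the new surgeon sentence will contradict them. It should also say that the 30% is cumulative to the last round, if that is what is meant.

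The cost is wording only, with slightly less favourable stated figures and no added recruits. If the sponsor prefers to keep 20 per main group, the matching figure is 29 each: a panel of 83, six more recruits, and up to 6 × $75 = $450 in honoraria. That option is not required, and the surgeon sentence would be needed either way.

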Appendix 1. Scoping Review MEDLINE Search Strategy

Ovid MEDLINE(R) and Epub Ahead of Print, In-Process, In-Data-Review & Other Non-Indexed Citations, Daily and Versions <1946 to March 16, 2022>

#	Query	Results from 17 Mar 2022
1	exp Anesthesia/	200,448
2	exp Anesthetics/	255,070
3	Anesthesiology/	32,529
4	Anesthesia Recovery Period/	5,440
5	(an?esthesia* or an?esthetic* or an?esthesiolog*).tw,kf.	323,470
6	or/1-5	539,493
7	exp Perioperative Care/	157,136
8	Perioperative Medicine/	92
9	(perioperative adj2 (car* or medicine* or period*)).tw.	17,106
10	(perioperative and (car* or medicine* or period*)).kf.	2,218
11	or/7-10	170,469
12	Patient Comfort/	567
13	Patient Safety/	24,260
14	Patient Satisfaction/	87,426
15	(patient* adj2 (comfort* or safet* or satisfaction*)).tw.	95,583
16	(patient* and (comfort* or safet* or satisfaction*)).kf.	13,730
17	Patient Reported Outcome Measures/	11,066
18	(patient reported adj4 (outcome measure* or experience measure*)).tw.	8,214
19	(patient reported and (outcome measure* or experience measure*)).kf.	3,051
20	Postoperative Complications/	389,613
21	Intraoperative Complications/	33,217
22	((peroperative ¹ or postoperative or intraoperative) adj2 complication*).tw.	90,933
23	((peroperative or postoperative or intraoperative) and complication*).kf.	10,527
24	Outcome Assessment, Health Care/	79,846
25	((health care or healthcare) adj4 outcome assessment*).tw.	27
26	((health care or healthcare) and outcome assessment*).kf.	1,119
27	or/12-26	719,962
28	6 and 11 and 27	6,932
29	exp animals/ not humans.sh.	4,973,232
30	28 not 29	6,842
31	(child* or adolesc* or pediat* or paediat*).jn.	281,321

¹ This is not a misspelled word, the MeSH term uses this wording.

Development of a standardized set of core metrics to assess the quality of anesthesia, perioperative care, and acute pain management in Canada: scoping review and multidisciplinary consensus Delphi study

32	30 not 31	6,679
33	exp case-control studies/	1,296,071
34	(case\$ and control\$).tw.	557,532
35	(case\$ and series).tw.	213,282
36	case reports.pt.	2,255,114
37	(case\$ adj2 report\$).tw.	638,230
38	(case\$ adj2 stud\$).tw.	282,881
39	(comment or editorial or letter).pt.	2,044,294
40	opinion piece.tw.	447
41	or/33-40	5,990,942
42	32 not 41	4,949
43	limit 42 to english language	3,816
44	limit 43 to yr="2015 -Current"	1,200

Development of a standardized set of core metrics to assess the quality of anesthesia, perioperative care, and acute pain management in Canada: scoping review and multidisciplinary consensus Delphi study

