The search strategy for this review aims to identify both published and unpublished studies. A three-step search strategy will be utilized. An initial limited search of MEDLINE (Ovid) will be undertaken followed by an analysis of the text words contained in the titles and abstracts, and of the indexed terms used to describe the articles. A second full search strategy using all identified keywords and indexed terms will then be undertaken on MEDLINE (Ovid) and across all other databases. The other databases to be searched will include MEDLINE (Ovid), Embase (Ovid), CINAHL (EBSCOhost), Web of Science, and Cochrane Database of Systematic Reviews (Ovid). Third, the reference list of all identified reports and articles will be searched for additional studies.

Studies from 2015/Jan-2022/March will be considered for inclusion in this review. This start date was chosen because end of 2014 was the end date of the last comprehensive searches in this area from previous studies (4,14). Only articles published in English will be included because of a lack of resources for translating non-English articles. Also, grey literature including guidelines, and existing evaluation metrics used by Canadian departments for quality assurance and improvement will be searched.

Development of a standardized set of core metrics to assess the quality of anesthesia, perioperative care, and acute pain management in Canada: scoping review and multidisciplinary consensus Delphi study

Inclusion criteria:

- Human adults

Note that this was conducted using search terms that excluded journal names in the field of pediatric patients. First, the filters for “adult” are not the same for all databases that will be searched. For instance, the limit for adult on MEDLINE (Ovid) is age 19+ years and Embase (Ovid) is 18 to 64 years. Second, we found that some articles were not indexed by the age filter, which we did not wish to miss. As such, we will manually filter for articles with an adult age group (18+).

- Must involve surgical patients requiring the presence of an anesthesiologist for anesthetic care, specifically for inpatients undergoing non-cardiac surgery.

Note that cardiac surgery is not included as an exclusion in the search strategy but rather will be manually excluded during screening, as we found using search filters excluded non-cardiac surgeries.

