- Must include at least one metric, with at least one definition for the metric. We will include patient-reported outcome and patient-reported experience measures, Canadian guidelines, and Canadian Anesthesiologists’ Society recommended practice standards. *Since there is an ongoing umbrella review registered on PROSPERO (15), we excluded quality indicators from the database search strategy and will use the results directly from the review. Since the umbrella review only included systematic reviews and may not account for metrics in recent guidelines and clinical use, we will include quality indicators from our grey literature search.*

- Published or in clinical use within the past 7 years (2015/Jan to 2022/March), to focus on contemporary metrics and because end of 2014 was the end date of the last comprehensive search in this area (14).

Note that only the latest version of guidelines will be included.

- For published studies only: full-text articles, study types being only experimental and epidemiological study designs (including randomized control trials, non-randomized control trials, quasi-experimental studies, before and after studies, prospective and retrospective cohort studies, case-control studies, and analytical cross-sectional studies), scoping/systematic review, and/or meta-analysis.

Exclusion criteria:

- For published studies only: we will exclude articles that are case reports, case series, letters, opinion pieces, commentaries, or editorials.

Due to the availability of multiple reviews and consensus guidelines, these article types will likely not contribute relevant additional information that is not already covered by other included sources. Study protocols are not excluded as they may contain metrics being used in contemporary original research.

- Studies reporting on ambulatory or outpatient surgery (i.e., those who do not require at least an overnight stay).
- Articles published in a language other than English.

Development of a standardized set of core metrics to assess the quality of anesthesia, perioperative care, and acute pain management in Canada: scoping review and multidisciplinary consensus Delphi study

Grey literature search:

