Appendix 2. Scoping Review data extraction form

Extractor 1 initial	
Extractor 2 initial	
Citation details	
Title	
Author	
Year	
Doi link	
Publication type	Multiple choice: systematic review +/- meta-analysis, scoping review, other review type, randomized control trials, non-randomized controlled trials, quasi-experimental studies, retrospective cohort, prospective cohort, before and after studies, case-control studies, analytical cross-sectional studies, guideline, departmental metric, other (free text)
Participants	
Country	
Region(s)	
Hospital setting	Academic vs. non-academic Urban vs. regional vs. rural
Population (e.g. disease, age group, etc)	
Sample size	
Surgery type(s)	
Duration of follow-up	
Age (mean)	
Age (median)	
Age (standard deviation)	
Age (range)	
Sex or gender	
American Society of Anesthesiologists Physical Status	
Length of stay	
Other demographics information	
Metric(s) information	
Please fill in the below for each complication investigated in the study	
Metric name	
Donabedian category	Structure, process, and outcomes - Can select multiple
How was the metric defined?	
How was the metric validated in this study? If not available, what references were cited in this study from previous validations?	

Development of a standardized set of core metrics to assess the quality of anesthesia, perioperative care, and acute pain management in Canada: scoping review and multidisciplinary consensus Delphi study

Measurement instrument for the metric (e.g. questionnaire name, special equipment, AIMS, history, physical exam, imaging, lab test)	
Mode of delivery of the measurement instrument (e.g. paper questionnaire, emailed; online tool, EHR extraction)	
Timepoint(s) of measurement	
Response rate(s)	
Any additional comments or results in the study related to feasibility. If not, what references were cited in this study from previous feasibility studies?	
Any additional results related to reliability. If not, what references were cited in this study from previous publications?	
Sampling strategy used for the metric (e.g. everyone, random sampling, stratified, etc.)	
Any other potentially relevant information

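### The only printed search strategy removes case-control studies, which the eligibility criteria accept, before anyone screens them

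*Combined protocol and SAP*

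**What the plan says.** The inclusion criteria for the scoping review list the published designs that qualify, among them "prospective and retrospective cohort studies, case-control studies, and analytical cross-sectional studies". The exclusion criteria are narrower: for published studies, "we will exclude articles that are case reports, case series, letters, opinion pieces, commentaries, or editorials". The reason offered is that "these article types will likely not contribute relevant additional information that is not already covered by other included sources", which speaks only to the types just listed. In Appendix 2, the publication-type options include "before and after studies, case-control studies, analytical cross-sectional studies, guideline, departmental metric".

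Appendix 1 prints one strategy, for MEDLINE. Line 33 is the subject heading "exp case-control studies". Line 34 takes any record with a word beginning case and a word beginning control in the searched text. Line 35 does the same for case and series. Line 38 takes case within two words of stud. Lines 33 to 40 are combined in line 41, and line 42 subtracts that set from line 32. The English and 2015-onward limits follow.

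The Search strategy section calls Appendix 1 an initial search and then states: "A second full search strategy using all identified keywords and indexed terms will then be undertaken on MEDLINE (Ovid) and across all other databases". That fuller strategy is not printed.

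**The concern.** A design that the criteria accept is taken out by the search itself. Under Article selection, two independent reviewers judge records against the stated criteria. Records lost at line 42 never reach them and would not appear as screening exclusions in the flow diagram. The reported process would then differ from the stated one.

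The loss need not stop at case-control studies. Without adjacency, line 34 removes a trial whose abstract mentions cases in one sentence and a control group in another. Line 35 acts in the same way on any abstract that uses both case and series.

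What is at stake is mainly the evidence reported for each metric. The analysis section promises validation, number of patients, population and study types per metric. That evidence can be incomplete even when the metric itself arrives by another route.

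**Working it through.** **1. Criteria against search lines**

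| Article type | Inclusion/exclusion criteria | Appendix 2 form | Appendix 1 NOT block |
|---|---|---|---|
| Case-control study | Eligible | Has a category | Removed (lines 33, 34, 38) |
| Trial, cohort or review using both case and control, or case and series, anywhere in the searched text | Eligible | Has a category | Removed (line 34 or 35) |
| Case report, letter, commentary, editorial, opinion piece | Excluded | No named category | Removed (lines 36, 37, 39, 40) |
| Case series | Excluded | No named category | Removed (line 35, too broadly) |

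The first two rows conflict, and no section explains why.

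**2. Are the printed counts coherent?** Lines 33 to 40 sum to 1,296,071 + 557,532 + 213,282 + 2,255,114 + 638,230 + 282,881 + 2,044,294 + 447 = 7,287,851. Their union, line 41, is 5,990,942. It lies between the largest component (2,255,114) and the sum, as it must.

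**3. Are the disputed lines redundant with the legitimate ones?** Across the whole database, lines 35, 36, 37, 39 and 40 sum to 5,151,367. So at least 5,990,942 − 5,151,367 = 839,575 records are in the NOT set only because of lines 33, 34 or 38. If line 35 is also treated as disputed, lines 36, 37, 39 and 40 sum to 4,938,085 and the bound becomes 5,990,942 − 4,938,085 = 1,052,857. The disputed lines therefore do separate work. These bounds are for the whole database and do not count losses within this search.

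**4. Effect within this search.** Line 32 has 6,679 records and line 42 has 4,949. Removed: 6,679 − 4,949 = 1,730, and 1,730 / 6,679 = 25.9%. The overlap of each single line with line 32 is not printed, so the eligible part is only known to lie between 0 and 1,730.

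**5. After the language and date limits.** Retained records pass at 3,816 / 4,949 = 77.1% (English) and then 1,200 / 3,816 = 31.4% (2015 onward), together 1,200 / 4,949 = 24.2%. If removed records passed at the same rate (an assumption), the whole block would remove 1,730 × 1,200 / 4,949 ≈ 419 records beside the 1,200 kept. The disputed lines account for an unknown part of these.

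**The case against.** The strongest reply is that Appendix 1 is only an initial search. A fuller one is planned, reference lists will be searched, and metrics also come from existing reviews, guidelines and departmental lists. Where a systematic review covers a category, only later articles are extracted. More than 200 potential metrics are to be cut to about 50, so a few missing studies may change nothing. All of this stands as a limit on the consequence. It does not remove the conflict: this is the only strategy printed, and the plan does not say whether the NOT block is dropped or carried into the full search or the other databases.

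A second reply is that 1,730 and 419 describe the whole block, most of which may be rightly excluded, and that 419 rests on an untested pass rate. That is correct, and both figures should be read only as ceilings, the second under its assumption.

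A third concerns consistency with the plan's other filters. For cardiac surgery, the plan rejects a search filter; such records "rather will be manually excluded during screening, as we found using search filters excluded non-cardiac surgeries". For age, it declines the database limits because "we found that some articles were not indexed by the age filter, which we did not wish to miss", but it still subtracts paediatric journal names at lines 31 and 32 (6,842 − 6,679 = 163 records). The cardiac example fully supports hand screening over filtering; the age example does so only in part.

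Finally, line 37 (case within two words of report) could also catch an eligible abstract that speaks of reported cases. That is possible, but the line has adjacency and is aimed at an excluded type, so it is a smaller matter.

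**Conclusion.** The concern holds. The eligibility criteria, the extraction form and the printed search cannot all be right, because the search applies a design exclusion that the other two contradict. Lines 34 and 35 can also remove other eligible designs by their own logic. The ceiling is 1,730 records before limits, or about 419 after limits if removed records behave like retained ones. The eligible loss inside those ceilings may be zero and cannot be narrowed from the documents. The effect on the list put to the Delphi panel is uncertain, and no lost metric is demonstrated. Confidence is high in the contradiction and does not extend to its downstream effect. It should be corrected because the repair is simple and the present text could carry the error into the full search.

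**What to change.** Take lines 33 and 34 out of line 41. Narrow line 38 to the adjacent phrase case study or case studies, so that it no longer catches case-control studies. Replace line 35 with an adjacency search for case series. Leave lines 36, 37, 39 and 40. Re-run from line 42 with the English limit and the stated January 2015 to March 2022 window, screen the restored records against the criteria, and report how many there were. State whether the full search and the other databases use a NOT block; where they do, use the corrected one.

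If case-control studies are meant to be left out, say so in the inclusion criteria and in Appendix 2, with a reason, and still tighten lines 34, 35 and 38.

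The cost is four edited lines, a re-run in MEDLINE and in any other database that uses the block, and extra dual screening of titles and abstracts. For MEDLINE the extra load is at most 1,730 records before limits, or about 419 after limits under the pass-rate assumption. For the other databases the documents give no counts.
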